2.8.4.3 Bone Marrow Examination

Following bone marrow examination data will be listed.

- Bone marrow aspiration
- Bone marrow biopsy
- Chromosomal test (Karyotype)
- Peripheral blood smear test

2.9 Pharmacokinetic endpoints

PAS will be used in all pharmacokinetic data analyses and PK summary statistics. In the case of samples taken are not within the time windows around the scheduled time points. These samples will exclude from the descriptive statistic which are summarized by time point, but will include in the non-compartmental analysis.

PK summary analyses will not be reproduced for final CSR.

PK parameters for subjects with extensive PK samples

The PK parameters that will be determined are shown in [Table 2-4](#). PK parameters of eltrombopag, including but not limited to those listed in Table 2-4, will be calculated from the individual concentration-time profile obtained following the administration of the study treatment and listed by subject.

Table 2-4 Non-compartmental PK parameters

AUClast	The AUC from time zero to the last measurable concentration sampling time (tlast) (mass*time*volume ⁻¹)
AUCtau	The AUC calculated to the end of a dosing interval (tau) at steady-state (amount*time*volume ⁻¹)
Cmax	The maximum (peak) observed plasma drug concentration after single dose administration (mass*volume ⁻¹)
Tmax	The time to reach maximum (peak) plasma drug concentration after single dose administration (time)
Ctrough	Pre-dose concentration at the end of dose interval (mass*volume ⁻¹)
CLss/F	Apparent systemic (or total body) clearance at steady state from plasma (volume/time)

Descriptive statistics (n, arithmetic mean, CV% mean, standard deviation (SD), median, geometric mean, CV% geo-mean, minimum and maximum) will be presented for PK analysis set for all PK parameters defined above except Tmax, where only n, median, minimum and maximum will be presented.

PK concentrations

Descriptive statistics including mean (arithmetic and geometric), SD, CV (arithmetic and geometric), median, minimum and maximum for PK concentration will be presented by dose, visit/sampling time point, including the frequency (n, %) of concentrations below the LLOQ and reported as zero.

The geometric mean and arithmetic mean (SD) concentration-time profiles will also be graphically presented. In addition, individual concentration-time profiles will be displayed graphically.

[figure not shown]
In addition, PK concentrations of eltrombopag for subjects with sparse PK samples will be summarized by dose, visit and scheduled time point.

All individual plasma eltrombopag concentration data will be listed by dose, visit and scheduled time point.

Handling of PK data below LLOQ or missing

All concentration values below the lower limit of quantitation (LLOQ) are set to zero by the Bioanalyst, and will be displayed in the listings as zero and flagged. LLOQ values will be treated as zero in any calculations of summary statistics, and treated as missing for the calculation of the geometric means and their CV%. The number of non-zero concentrations will also be reported in the summary statistics.

Missing values for any PK data will not be imputed and will be treated as missing.

2.11 Patient-reported outcomes

There will be no patient-reported outcome analysis planned in this study.

2.12 Cytogenetic abnormalities and clonal evolution

Clonal cytogenetic evolution will be evaluated during the study, and the rate of the subjects who developed any clonal evolution including clonal evolution to PNH, evolution to AML or MDS etc. will be calculated.

2.14 Interim analysis

There will be no formal interim analysis planned in this study.

3 Sample size calculation

As this is a bridging study to support China registration, an estimation strategy rather than formal hypothesis testing will be pursued. Approximately 20 subjects will be enrolled into the study based on the feasibility rather than statistical considerations. This number of subjects is considered appropriate to assess the efficacy and safety of eltrombopag in Chinese patients.

3.1 Primary analysis

The hematologic response rate at Week 24 in the pivotal study of NIH-09-H-0154 was 40%. Assuming a same response rate (40%) in Chinese subjects, the 90% confidence interval of the hematological response rate with a total of 20 subjects will be (21.7%, 60.6%).

Below table shows the 90% CIs for various observed response rate. The maximum half-width of the 90% CIs is 19.8%.

Table 3-1 90% CIs for various observed response rate

Sample size	# of responders	Hematologic response rate (%)	90% CI (%)
20	4	20	(7.1, 40.1)
20	6	30	(14.0, 50.8)
20	8	40	(21.7, 60.6)

Sample size	# of responders	Hematologic response rate (%)	90% CI (%)
20	10	50	(30.2, 69.8)

The 12 evaluable subjects for intensive PK sampling was chosen based on feasibility and practical considerationzs to assist in characterizing the PK of eltrombopag in Chinese subjects.

4 Change to protocol specified analyses

No change from protocol specified analysis was made.

5 Appendix

5.1 Imputation rules

5.1.1 Study drug

The following rule should be used for the imputation of the dose end date for a given study treatment component:

Scenario 1: If the dose end date is completely missing and there is no EOT page and no death date, the patient is considered as on-going:

The patient should be treated as on-going and the cut-off date should be used as the dose end date.

Scenario 2: If the dose end date is completely or partially missing and the EOT page is available:

Case 1: The dose end date is completely missing, and the EOT completion date is complete, then this latter date should be used.

Case 2: Only Year(yyyy) of the dose end date is available and yyyy < the year of EOT date:

Use Dec31yyyy

Case 3: Only Year(yyyy) of the dose end date is available and yyyy = the year of EOT date:

Use EOT date

Case 4: Both Year(yyyy) and Month (mm) are available for dose end date, and yyyy = the year of EOT date and mm < the month of EOT date:

Use last day of the Month (mm)

All other cases should be considered as a data issue.

After imputation, compare the imputed date with start date of treatment, if the imputed date is < start date of treatment: Use the treatment start date

Patients with missing start dates are to be considered missing for all study treatment component related calculations and no imputation will be made. If start date is missing then end-date should not be imputed.

5.1.2 AE, ConMeds and safety assessment date imputation

Table 5-1 Imputation of start dates (AE, CM) and assessments (LB, EG, VS)

Missing Element	Rule
day, month, and year	
• No imputation will be done for completely missing dates
day, month	
• If available year = year of study treatment start date then
◦ If stop date contains a full date and stop date is earlier than study treatment start date then set start date = 01JanYYYY
◦ Else set start date = study treatment start date.• If available year > year of study treatment start date then 01JanYYYY• If available year < year of study treatment start date then 01JulYYYY
day	
• If available month and year = month and year of study treatment start date then
◦ If stop date contains a full date and stop date is earlier than study treatment start date then set start date= 01MONYYYY.
◦ Else set start date = study treatment start date.• If available month and year > month and year of study treatment start date then 01MONYYYY• If available month and year < month year of study treatment start date then 15MONYYYY

Table 5-2 Imputation of end dates (AE, CM)

Missing Element	Rule (*=last treatment date plus 30 days not > (death date, cut-off date, withdrawal of consent date))
day, month, and year	
• Completely missing end dates (incl. ongoing events) will be imputed by the end date of the on-treatment period*
day, month	
• If partial end date contains year only, set end date = earliest of 31DecYYYY or end date of the on-treatment period *
day	
• If partial end date contains month and year, set end date = earliest of last day of the month or end date of the on-treatment period*

Any AEs and ConMeds with partial/missing dates will be displayed as such in the data listings.

Any AEs and ConMeds which are continuing as per data cut-off will be shown as 'ongoing' rather than the end date provided.

The above imputations are only used for analyses of time to and duration of AEs and concomitant medications.

5.1.2.1 Other imputations

Incomplete date of initial diagnosis of SAA and date of most recent recurrence

Missing day is defaulted to the 15th of the month and missing month and day is defaulted to 01-Jan.

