2.1.3 General definitions

Study drug and Study treatment

The study drug/study treatments for this study is eltrombopag (ETB115).

Eltrombopag will be supplied as film-coated tablets (25 mg) provided either as commercial packages locally.

Date of first administration of study treatment

The date of first administration of study treatment will be derived as the first date when a nonzero dose of study treatment is administered and recorded on the appropriate CRF.

Date of last administration of study treatment

The date of last administration of study treatment will be derived as the last date when a nonzero dose of study treatment is administered and recorded on the appropriate CRF. For those patients still on treatment at cutoff date, the cutoff date will be imputed as the date of last administration of study treatment.

Study day

The study day, describes the day of the event or assessment date, relative to the reference start date.

The study day is defined as:

- The date of the event (visit date, onset date of an event, assessment date etc.) – reference start date + 1 if event is on or after the reference start date;
- The date of the event (visit date, onset date of an event, assessment date etc.) – reference start date if event precedes the reference start date.

The reference date for all assessments (safety, efficacy, pk, etc) is the date of first administration of study treatment as defined above. The study day will be displayed in the data listings.

Time unit

A year length is defined as 365.25 days. A month length is 30.4375 days (365.25/12). If duration is reported in months, duration in days will be divided by 30.4375. If duration is reported in years, duration in days will be divided by 365.25.

Baseline

For safety and efficacy evaluations, the last available assessment on or before the date of first administration of study treatment is defined as “baseline” assessment. If patients have no value as defined above, the baseline result will be missing.

On-treatment assessment/event and observation periods

The overall observation period will be divided into three mutually exclusive segments:

1. ***pre-treatment period***: from day of patient's informed consent to the day before first administration of study treatment
2. ***on-treatment period***: from date of first administration of study treatment to 30 days after date of last actual administration of study treatment (including start and stop date)

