2.3.1 Basic demographic and baseline characteristics

All demographic data will be summarized and listed. Categorical data (e.g. gender, age groups: 18-64 years, ≥ 65 years, others as applicable) will be summarized by frequency counts and percentages; the number and percentage of patients with missing data will be provided. Continuous data (e.g. age, weight, height) will be summarized by descriptive statistics (N, mean, median, standard deviation, minimum and maximum).

Haematological parameters at the assessment of patients eligibility including platelet count, haemoglobin, absolute neutrophils count (ANC) and absolute reticulocytes count (ARC) will be summarized by descriptive statistics (N, mean, median, standard deviation, minimum and maximum). RBC and Platelet Transfusion (Independence and Dependence), and G-CSF injection required (Yes/No) at baseline will be summarized by frequency counts and percentages.

The following other baseline characteristics will be summarized by frequency counts and percentages:

- Relapsed patients, refractory patients and patients who achieved PR after the last course of IST with platelet count $<30 \times 10^9 / L$,
- Concomitant use of CsA and anabolic steroids at baseline: Yes, No,
- Prior ATG/ALG Therapies: Yes, No.

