2.3.2 Diagnosis and extent of SAA

Summary statistics will be tabulated for diagnosis and extent of SAA. This analysis will include the following if they are available: stage at initial diagnosis, time since initial diagnosis, time

from initial diagnosis to first recurrence/progression (in months), and time since most recent relapse/progression to first dose (in months).

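### Year-only SAA diagnosis and recurrence dates default to 01-Jan, so disease-history times ending at first dose run about 6 months long per affected date

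*SAP*

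**What the plan says.** SAP 5.1.2.1 covers two dates: "Incomplete date of initial diagnosis of SAA and date of most recent recurrence". Its whole rule is "Missing day is defaulted to the 15th of the month and missing month and day is defaulted to 01-Jan". No check on the order of dates follows.

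SAP 2.3.2 lists the summaries that use such dates, to be produced where the data exist. Besides how long ago SAA was diagnosed, it names two further intervals: "from initial diagnosis to first recurrence/progression (in months), and time since most recent relapse/progression to first dose (in months". The end point of the time since diagnosis is not stated; I take it to be first dose. The diagnosis interval runs to the first recurrence, whereas 5.1.2.1 names only the most recent one.

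Two nearby rules are built differently. For adverse events, concomitant medications and safety assessments, one branch of Table 5-1 in SAP 5.1.2 reads "If available year < year of study treatment start date then 01JulYYYY". For the dose end date, SAP 5.1.1 has an order check that replaces an impossible value: "After imputation, compare the imputed date with start date of treatment, if the imputed date is < start date of treatment: Use the treatment start".

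SAP 2.3 says that the SAA diagnosis and extent analysis is not repeated for the final CSR. It does repeat the baseline blood counts, because a derivation for missing reticulocyte counts was added.

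**The concern.** The two defaults follow different principles. A missing day goes to about the middle of its possible range, which costs almost nothing on average. A missing day and month goes to the very start of the range. Any interval that begins at such a date and ends at first dose can then only be lengthened, never shortened.

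The intervals in SAP 2.3.2 tell a reader how long-standing the disease was and how recent the last relapse was. In a single-arm study of about 20 patients, which include a relapsed group (SAP 2.3.1: "Relapsed patients, refractory patients and patients who achieved PR after the last course of IST"), a few such dates can visibly move a mean. Without an order check, the table can also contain a recurrence before diagnosis, which would show up as the reported minimum.

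**Working it through.** The plan gives no figure for this error, so there is none to reproduce.

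**Inputs**
- Default for unknown month and day: 01-Jan (SAP 5.1.2.1).
- Month length: 30.4375 days (SAP 2.1.3).
- Planned size: about 20 patients (SAP 3).
- Assumption, not in the documents: the true date is uniform over the calendar year.
- Assumption, not in the documents: the number k of patients with a year-only date, shown as a range.

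**1. Error per imputed date.** The error is the true date minus the imputed date.
- 01-Jan, 365-day year: mean of 0 to 364 = 182.0 days; 182.0 / 30.4375 = 5.98 months.
- 01-Jan, 366-day year: 182.5 / 30.4375 = 6.00 months. The range in either case is 0 to about 12.0 months.
- 01-Jul, 365-day year: 182 − 181 = 1 day = 0.03 months. In a 366-day year it is 0.5 day = 0.02 months. The mean absolute error falls from about 6.0 to 3.0 months.

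**2. Relapse in the same year as first dose.** If first dose is on day f of the year, the relapse can lie only on days 1 to f, so the mean overstatement is (f − 1)/2 days.

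| First dose on day | Mean overstatement (months) |
|---|---|
| 91 | 45 / 30.4375 = 1.5 |
| 182 | 90.5 / 30.4375 = 3.0 |
| 274 | 136.5 / 30.4375 = 4.5 |
| 365 | 182 / 30.4375 = 6.0 |

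**3. Shift in the mean time since diagnosis, 20 patients:** (k / 20) × 5.98 months.

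| k | 1 | 2 | 5 | 10 | 20 |
|---|---|---|---|---|---|
| Shift (months) | 0.3 | 0.6 | 1.5 | 3.0 | 6.0 |

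For relapse to first dose, the divisor is the number of patients with a relapse date, which the documents do not give.

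**4. Diagnosis to recurrence.**
- Only diagnosis imputed: about +6.0 months on average.
- Only recurrence imputed: about −6.0 months on average.
- Both imputed: about 0 on average, and exactly 0 months if both fall in one year.

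Example of a negative value: diagnosis on 20-Mar-2018, recurrence recorded as 2018. The recurrence becomes 01-Jan-2018, and the interval is −78 days, or −78 / 30.4375 = −2.6 months.

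With a known diagnosis date uniform over the year and only the recurrence imputed, the chance of a negative value is roughly 1 − (true gap in months)/12. A simulation with one million draws per gap agrees:

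| True gap (months) | Negative, 01-Jan | Negative, 01-Jul |
|---|---|---|
| 3 | 75% | 25% |
| 6 | 50% | 0.3% |
| 9 | 25% | 0% |
| 12 or more | 0% | 0% |

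So a mid-year default alone does not remove every negative value; an order check is needed as well. The missing-day rule needs it too: the 15th can fall after a first dose given earlier in that month.

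**The case against.** The strongest reply is that exposure is probably small. Inclusion criterion 2 (Protocol 5.1) relies on marrow and blood findings at diagnosis, Protocol 11.3 requires source verification of eligibility, and Protocol 11.2 provides for queries on missing values. Dated diagnosis records should therefore usually exist. That is inference, but nothing in the documents points the other way, and the count of year-only dates may be zero. SAP 2.1.2 also reports the median, which a few shifted dates move less than the mean. This stands, and it limits the importance of the point.

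A reader might infer that the SAP contradicts itself, because Table 5-1 uses 01-Jul for earlier years. It does not. SAP 5.1.2 restricts those imputations to the timing and duration of adverse events and concomitant medications, and Table 5-1 uses 01-Jan in other branches. The table shows only that a mid-year default is already in use in this SAP. It is also true that a year-only default of 01-Jan cannot fall after first dose, while 01-Jul can, so the replacement needs a bound.

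A reader might also infer that the rule weakens the case against spontaneous recovery or the bridge to the US and Japanese studies. The documents do not support that. Protocol 4.1.2 rests the first argument on the 6 months without ATG/ALG, alemtuzumab or cyclophosphamide, and it describes bridging through pharmacokinetics and exposure. No planned analysis compares disease duration across studies, and duration is not a subgroup in SAP 2.2.1.

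Negative times need several conditions at once: diagnosis and recurrence in one calendar year, a year-only recurrence date, and a first recurrence that is also the most recent, unless the rule is applied to a date it does not name.

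**Conclusion.** The point holds in a narrow form. As written, the rule moves each year-only SAA date about 6 months too early on average. It therefore lengthens the two intervals that end at first dose, by less for relapses in the first-dose year. The size rests on the uniform-date assumption and on first dose as the end point of the time since diagnosis.

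It would be wrong to read this as disease-history times being 6 months too long across the table. The figure is per affected date, and the shift in the mean ranges from nothing to 6.0 months according to a count that the documents do not give. Nor is every interval overstated, because diagnosis to recurrence is understated when only the recurrence is imputed. The mismatch between first recurrence (2.3.2) and most recent recurrence (5.1.2.1) is a small gap that should be closed in any case.

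Only descriptive baseline summaries are touched. The primary endpoint is unaffected. Low priority.

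**What to change.** In SAP 5.1.2.1:

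1. Default a missing month and day to 01-Jul.
2. State that the rule also covers the date of first recurrence used in 2.3.2.
3. Bound imputed dates so that recurrence is not before diagnosis and no date is after first dose. Where a bound applies, the interval can become zero (for example, relapse to first dose when first dose is before July of the relapse year), so count bounded dates as well.
4. Footnote the SAA history table with the number of imputed dates.

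State in 2.3.2 that the time since diagnosis ends at first dose, if that is meant.

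Rerun the SAA history table only if a year-only date was imputed or an order check fails. SAP 2.3 already makes such an exception for the baseline blood counts. If neither applies, one sentence saying so closes the point. The cost is a few sentences in the SAP and, at most, one baseline table.

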5.2 AEs coding/grading

Adverse events are coded using the Medical dictionary for regulatory activities (MedDRA) terminology.

AEs will be assessed according to the Common Terminology Criteria for Adverse Events (CTCAE) version 4.03.

The CTCAE represents a comprehensive grading system for reporting the acute and late effects of cancer treatments. CTCAE grading is by definition a 5-point scale generally corresponding to mild, moderate, severe, life threatening, and death. This grading system inherently places a value on the importance of an event, although there is not necessarily proportionality among grades (a grade 2 is not necessarily twice as bad as a grade 1).

5.3 Laboratory parameters derivations

Grade categorization of lab values will be assigned programmatically as per NCI Common Terminology Criteria for Adverse Events (CTCAE) version 4.03 (specify version used in the RAP). The calculation of CTCAE grades will be based on the observed laboratory values only, clinical assessments will not be taken into account. The criteria to assign CTCAE grades are given in Novartis internal criteria for CTCAE grading of laboratory parameters. The latest available version of the document based on the underlying CTCAE version 4.03 at the time of analysis will be used.

For laboratory tests where grades are not defined by CTCAE v4.03, results will be graded by the low/normal/high (or other project-specific ranges, if more suitable) classifications based on laboratory normal ranges.

A severity grade of 0 will be assigned for all non-missing lab values not graded as 1 or higher. Grade 5 will not be used. For laboratory tests that are graded for both low and high values, summaries will be done separately and labelled by direction, e.g., sodium will be summarized as hyponatremia and hypernatremia.

For Reticulocyte absolute count which are missing, the following rules will be applied to derive them:

Reticulocyte (absolute count in 10E9/L) = Reticulocyte count % * RBC count in SI unit (10E12/L) * **10**.

Imputation Rules

CTC grading for blood differentials is based on absolute values. However, this data may not be reported as absolute counts but rather as percentage of WBC.

If laboratory values are provided as ‘<X’ (i.e. below limit of detection) or ‘>X’, prior to conversion of laboratory values to SI unit, these numeric values are set to X.

The following rules will be applied to derive the WBC differential counts when only percentages are available for a xxx differential

$$\text{xxx count} = (\text{WBC count}) * (\text{xxx \%value} / 100)$$

CTCAE grades for the derived absolute WBC differential counts will be assigned as described earlier.

